Appendix Table 2. Study Procedures Table (Open-Label Rollover Extension)

Study Procedures	End of Blinded Treatment Visit ^a	End of Week ^{e, l, o}								30-Day Follow-up ^k	Early Study Drugs DC ^c
		12 OL	24 OL	36 OL	48 OL	60 OL	72 OL	84 OL	96 OL		
Adverse Events	X	X	X	X	X	X	X	X	X	X ^f	X ^f
Concomitant Medications	X	X	X	X	X	X	X	X	X	X	X
Complete/Symptom-Directed Physical Exam	X	X ^d	X ^d	X ^d	X	X ^d	X ^d	X ^d	X	X ^{d, f}	X ^f
12-Lead ECG (performed supine)	X				X				X		
Vital signs (blood pressure, pulse, respiration rate, and temperature), including Weight	X	X	X	X	X	X	X	X	X	X	X
Urinalysis	X	X	X	X	X	X	X	X	X	X ^f	X ^f
Urine Pregnancy Test ^g	X	X	X	X	X	X	X	X	X	X	X
Chemistry Profile ^h	X	X	X	X	X	X	X	X	X	X ^f	X ^f
Metabolic Assessments ⁱ	X		X		X		X		X		
Estimated Glomerular Filtration Rate	X	X	X	X	X	X	X	X	X	X ^f	X
Hematology Profile ^j	X	X	X	X	X	X	X	X	X	X ^f	X ^f
Plasma HIV-1 RNA	X	X	X	X	X	X	X	X	X	X	X
CD4+ Cell Count	X	X	X	X	X	X	X	X	X	X	X
CCI											
HBV Blood Panel ^m			X ^m		X ^m		X ^m		X ^m		
Plasma HBV DNA ^m		X ^m	X ^m	X ^m	X ^m	X ^m	X ^m	X ^m	X ^m		
HCV Serology ⁿ					X ⁿ				X ⁿ		
HIV-1 Genotype/Phenotype ^e											X ^e
Study Drug Dispensation ^b	X ^b	X	X	X	X	X	X	X			
Study Drug Accountability	X	X	X	X	X	X	X	X	X		X

a Once the last subject completes the Week 144 visit and Gilead completes the Week 144 analysis, all subjects will return to the clinic (within 30 days ± 6 days) for an End of Blinded Treatment Visit. At the End of Blinded Treatment Visit, if safety and efficacy of B/F/TAF FDC is demonstrated following review of unblinded data, subjects in a country where GS-9883/F/TAF FDC is not available, will be given the option to receive B/F/TAF FDC in an open-label extension phase for up to 48 weeks, or until the product becomes accessible to subjects through an access program, or until Gilead Sciences elects to discontinue the study in that country, whichever occurs first.

- b Open-label study drug, B/F/TAF FDC will be dispensed to subjects participating in the Open-Label Rollover extension for up to 48 weeks.
- c Subjects who discontinue study drug during the open-label rollover extension portion of the study will be asked to return to the clinic within 72 hours of stopping study drugs for the Early Study Drugs Discontinuation Visit followed by a 30-Day Follow-Up Visit. The subject will not continue attending the scheduled study visits.
- d Symptom-directed physical examination as needed.
- e HIV-1 genotype and phenotype testing for subjects with virologic failure. Following virologic rebound, subjects will be asked to return to the clinic (2-3 weeks later) prior to the next scheduled visit or at the next scheduled study visit, for a HIV-1 RNA and HIV-1 genotype and phenotype (reverse transcriptase, protease, and integrase genotype and phenotype) blood draw. Based on the results of this testing, subjects should be managed according to the Virologic Rebound Schema (Protocol Section 6.12.1).
- f Any adverse event or test showing abnormal results that is believed to have a possible or probable causal relationship with the study drug will be repeated weekly (or as often as deemed prudent by the Investigator) until the abnormality is resolved, returns to Day 1, or is otherwise explained.
- g Females of childbearing potential only. Positive urine pregnancy tests will be confirmed with a serum test.
- h Chemistry profile: alkaline phosphatase, AST, ALT, GGT, total bilirubin, direct and indirect bilirubin, total protein, albumin, LDH, CPK, bicarbonate, BUN, calcium, chloride, creatinine, glucose, phosphorus, magnesium, potassium, sodium, uric acid and amylase (reflex lipase testing is performed in subjects with total amylase > 1.5 x ULN). At Week 24 OL and Week 48 OL, and End of Blinded Treatment Visit, analyses of glucose will be done as part of the fasting metabolic assessments and not as part of the chemistry profile. For all subjects, TSH will be done at the End of Blinded Treatment Visit, Week 24 OL, Week 48 OL, and Early Study Drug Discontinuation Visit.
- i Fasting (no food or drinks, except water, at least 8 hours prior to blood collection) glucose and lipid panel (total cholesterol, HDL, direct LDL, triglycerides) every 24 weeks. If the subject has not fasted prior to the visit, the visit may proceed, but the subject must return within 72 hours in a fasted state to draw blood for the metabolic assessments.
- j CBC with differential and platelet count.
- k Subjects who complete the open-label rollover extension will be required to return to the clinic 30 days after the completion of study drugs for the 30-Day Follow-Up Visit. Subjects who permanently discontinue study drugs during the open-label rollover extension will be asked to return to the clinic 30 days after the completion of the Early Study Drugs Discontinuation Visit for the 30-Day Follow-Up Visit. For the purpose of scheduling a 30-Day Follow-Up Visit, a ± 6 days window may be used.
- l Study visits are to be completed within ± 2 days of the protocol-specified visit date based on the End of Blinded Treatment Visit date through Week 12 OL and completed within ± 6 days of the protocol-specified visit date every 12 weeks thereafter, unless otherwise specified
- m For subjects who meet the definition of HBV infection at any visit: The following will be conducted by the central laboratory: HBsAb, HBsAg (qualitative and quantitative) and HBeAg (if negative, reflex HBeAb) (every 24 weeks) and Plasma HBV DNA (every 12 weeks). For subjects who do NOT meet the definition of HBV infection at any visit: The following will be conducted by the central laboratory: Hepatitis B surface antibody (HBsAb), Hepatitis B virus core antibody (HBcAb), and Hepatitis B virus surface antigen serology (HBsAg). Subjects who are HBsAg and/or HBcAb positive will have a reflex test for HBV DNA (viral load) (Weeks 48 OL and 96 OL)
- n Hepatitis C virus (HCVAb) serology. Subjects who are HCVAb positive will have a HCV RNA test performed. (Weeks 48 OL and 96 OL).
- o After Week 96 OL, if subject is in a country where GS-9883/F/TAF is not available, the study procedures completed by the subject will be the same at every 48 weeks (i.e. OL Weeks 48, 96) and at every 12 weeks (i.e. OL Weeks 12, 24, 36, 60, 72, 84) until the product becomes accessible to subjects through an access program, or until Gilead Sciences elects to discontinue the study in that country, whichever occurs first.

Appendix 2. Cardiovascular or Cerebrovascular Events

An adverse event record will be flagged as a cardiovascular or cerebrovascular event if its MedDRA PT is included in the pre-specified PT list, which includes all PTs from the narrow search of the following 3 SMQs under MedDRA version 24.0 provided by Gilead GLPS and reviewed by Gilead medical monitors.

	SMQ Source
Cardiovascular or Cerebrovascular Events	Ischaemic central nervous system vascular conditions (SMQ) – Narrow Scope Term
	Myocardial infarction (SMQ) - Narrow Scope Term
	Other ischaemic heart disease (SMQ) - Narrow Scope Term

Appendix 3. Hepatic Events

An adverse event record will be flagged as a hepatic event if its MedDRA PT is included in the pre-specified PT list, which includes all PTs from the broad search of the following 15 SMQs under MedDRA version 24.0 provided by Gilead GLPS and reviewed by Gilead medical monitors.

	SMQ Source
Hepatic Events (HEP)	Biliary neoplasms benign (incl cysts and polyps) (SMQ)
	Biliary malignant tumours (SMQ)
	Biliary tumours of unspecified malignancy (SMQ)
	Biliary system related investigations, signs and symptoms (SMQ)
	Biliary tract disorders (SMQ)
	Gallbladder related disorders (SMQ)
	Gallstone related disorders (SMQ)
	Cholestasis and jaundice of hepatic origin (SMQ)
	Hepatic failure, fibrosis and cirrhosis and other liver damage-related conditions (SMQ)
	Hepatitis, non-infectious (SMQ)
	Liver neoplasms, benign (incl cysts and polyps) (SMQ)
	Liver malignant tumours (SMQ)
	Liver tumours of unspecified malignancy (SMQ)
	Liver related investigations, signs and symptoms (SMQ)
	Liver-related coagulation and bleeding disturbances (SMQ)

Appendix 4. Adverse Events of COVID-19

An adverse event record will be flagged as adverse events for COVID-19 if its MedDRA PT is included in the pre-specified PT list, which includes all PTs from the narrow search of the following COVID-19 SMQs under MedDRA version 24.0 provided by Gilead GLPS (search name: COVID-19 (SMQ) – Narrow) and reviewed by Gilead medical monitors.

	SMQ Source
AEs for COVID-19	COVID-19 (SMQ) (Narrow Scope)

Appendix 5. Determining Missing and Virtual Visits Due to COVID-19

This appendix describes the site collection of COVID-19 data as pertains to missed/virtual visits and the data processing algorithm used to determine which visits were missing and which visits were virtual.

Data collection

A COVID-19 supplement to the eCRF Completion Guidelines (CCG) was provided by data management to instruct clinical trial sites with respect to data entry expectations pertaining to scenarios related to the COVID-19 pandemic. If a visit was missed, sites should enter “Visit missed due to COVID-19.” If a visit which was to be conducted in-person was conducted virtually, sites should enter “Virtual visit due to COVID-19.”

Determination of Missed and Virtual visits

Natural Language Processing (NLP) was used to search the CRF comment fields to identify instances of “COVID-19” (or synonyms, see [Table X 1](#)) and “Virtual” (or synonyms, see [Table X 1](#)). The search terms are maintained in a global lookup and can be modified and/or corrected to tune the NLP model. For each comment field the following algorithm was applied:

STEP 1: Eliminate extraneous text from each comment field, e.g. “and”, “or”, “for”, etc. This is done using the list of extraneous terms given in [Table X 2](#).

STEP 2: Check each of the remaining comment text strings against the “COVID-19” terms and “Virtual” terms with the Levenshtein distance, using SAS function COMPGED (Computes a generalized edit distance using the Levenshtein operations to compute/summarize the degree of difference between two text strings):

- i. If Levenshtein distance < 149 for any of the “COVID-19” terms then COVIDFL = 1, else COVIDFL = 0
- ii. If Levenshtein distance < 149 for any of the “Virtual” terms then VIRTFL = 1, else VIRTFL = 0

STEP 3: For any comments with COVIDFL = 1, assign “Missed visit” or “Virtual visit as follows

- i. IF COVIDFL =1 and the visit date is missing then result is ‘Missed Visit’
- ii. IF COVIDFL =1 and VIRTFL = 1 then result is = ‘Virtual Visit’
- iii. Otherwise result is missing

Table X 1. Examples of search terms for “COVID-19” and “Virtual” used to identify missed and virtual visits

Search terms for “COVID-19”	Search terms for “Virtual”
COVID19	VIRTUAL
CORONA	TELEMED
CORONAVIRUS	TELEHEALTH
PANDEMIC	TELEPHONE
OUTBREAK	REMOTE
CRISIS	TELEMEDICINE
LOCKDOWN	TELECONSULTATION
QUARANTINE	TELEPHONICALLY
SHELTER	PHONE
	HOME VISIT
	ZOOM
	SKYPE

Table X 2. Examples of extraneous text terms to eliminate from the comment fields.

a	down	in	she'd	until
about	during	into	she'll	up
above	each	is	she's	very
after	few	it	should	was
again	for	its	so	we
against	from	it's	some	we'd
all	further	itself	such	we'll
am	had	i've	than	were
an	has	let's	that	we're
and	have	me	that's	we've
any	having	more	the	what
are	he	most	their	what's
as	he'd	my	theirs	when
at	he'll	myself	them	when's
be	her	nor	themselves	where
because	here	of	then	where's
been	here's	on	there	which
before	hers	once	there's	while
being	herself	only	these	who
below	he's	or	they	whom
between	him	other	they'd	who's
both	himself	ought	they'll	why
but	his	our	they're	why's
by	how	ours	they've	with
could	how's	ourselves	this	would
did	i	out	those	you
do	i'd	over	through	you'd
does	if	own	to	you'll
doing	i'll	same	too	your
down	i'm	she	under	you're
	you've	yourself	yourselves	yours

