4.4. Missing Protocol-Specified Information due to COVID-19

An overall summary of the number and percentage of subjects with missed or virtual visits (e.g., at least 1, with 1, 2, 3 or more visits) due to the COVID-19 pandemic will be provided. The denominator for the percentage calculation will be the total number of subjects in the all B/F/TAF analysis set.

A by-subject listing of subjects with missed or virtual visits due to COVID-19 will be provided by subject ID number in ascending order.

The determination of missing or virtual Visits due to COVID-19 was done using Natural Language Processing (NLP) to search the CRF comment fields. A detailed explanation of the algorithm is given in [Appendix 5](#).

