Regional Lab Center	Accession Number	Regular Regression for Correction (umol/L)	Inverse Conversion Formula (umol/L)
Indy	start with 65	$Y=1.002*X+1.77$	$Y=(X-1.77)/1.002$
GVA	start with 62 or 63	$Y=1.025*X+2.62$	$Y=(X-2.62)/1.025$
SHANGHAI	start with 67	$Y=0.971*X+5.42$	$Y=(X-5.42)/0.971$
SINGAPORE	start with 64 or 66	$Y=1.009*X-1.42$	$Y=(X+1.42)/1.009$
JAPAN	start with 68	$Y=1.033*X+7.25$	$Y=(X-7.25)/1.033$

Recalculate eGFR using the corrected serum creatinine, using the following formula:

$$eGFR_{CG} \text{ (mL/min)} = [(140 - \text{age (yrs)}) \times \text{weight (kg)} \times (0.85 \text{ if female})] / (\text{SCr (mg/dL)} \times 72),$$

where weight is total body mass in kilograms, and SCr is serum creatinine.

Here age refers to the age at the sample collection date. Use the derived visit to align serum creatinine and weight. For multiple records, choose the one with analysis flag

For this analysis, since serum creatinine samples were analyzed before lot change at Baseline, we only requested conversion to the results with previous lot for serum creatine and eGFR.

For the analysis of change from baseline in serum creatine and eGFR: the sample analyzed by updated calibration lot will be converted to the results assuming old calibration lot used as a new record. During ADaM stage, a derived parameter code (SCREA2) for “Serum Creatine before and after calibration change combined” and (EGFR2) for “eGFR before and after calibration change combined” will be generated to pool the records from both original and converted results to calculate the change from baseline in serum creatine and eGFR.

For the analysis of toxicity grade for serum creatine and eGFR: toxicity grade will be based on the Gilead grading results (ie, toxgrg) from original values before conversion. In another words, during ADaM stage, derived parameter codes (SCREATOX and EGFRTOX) for “Serum Creatine for Toxicity” and “eGFR for Toxicity” will be generated to pool the records from after calibration change and before calibration change to derive treatment-emergent toxicity grades, maximum postbaseline toxicity grades, etc.

24) Study and/or study drug discontinuations due to COVID-19

a) Study Drug Discontinuation

- Run NLP algorithm on the comment field from Study Drug Completion eCRF, checking for “COVID-19” text
- In COCOVID19 data set if COFORM = “Study Drug Completion”, then subject discontinued study drug due to COVID-19

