- If study drug discontinued due to an AE, check if corresponding AE flagged as a COVID-19

b) Study Discontinuation

- Run NLP algorithm on the comment field from general comments for “COVID-19” text
- In COCOVID19 data set if COFORM = “Study Completion”, then subject discontinued study due to COVID-19

If study discontinued due to an AE, check if corresponding AE flagged as a COVID-19

SAP-Final-GS-US-380-1490

ELECTRONIC SIGNATURES

Signed by	Meaning of Signature	Server Date (dd-MMM- yyyy hh:mm:ss)
PPD	Biostatistics eSigned	22-Sep-2021 19:58:08
PPD	Project Team Leader eSigned	22-Sep-2021 21:24:30

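### The SAP's COVID-19 text rules have no calendar limit and no check of the recorded reason, so unrelated missed visits and early discontinuations can be attributed to COVID-19

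*SAP*

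**What the plan says.** **Visits (SAP Appendix 5).** Sites were given a standard phrase to enter for a visit missed because of COVID-19, and another for one held remotely. A text search of the eCRF comment fields then sets two flags. The COVID flag is set by the rule "If Levenshtein distance < 149 for any of the" COVID-19 terms. The example list in Table X 1 contains specific words (COVID19, CORONAVIRUS) and general ones (OUTBREAK, CRISIS, SHELTER). The list is not fixed: "The search terms are maintained in a global lookup and can be modified and/or corrected to tune the NLP model".

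Step 3 classifies the visit. "IF COVIDFL =1 and the visit date is missing then result is" a missed visit; "IF COVIDFL =1 and VIRTFL = 1 then result is" a virtual visit; "Otherwise result is missing". No step mentions a calendar date.

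**Summary (SAP Section 4.4).** Subjects are tabulated by whether they had at least one such visit, and by one, two, or three or more. "The denominator for the percentage calculation will be the total number of subjects in the all B/F/TAF analysis set". A by-subject listing accompanies the table.

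**Discontinuations (SAP Appendix 6 item 24).** If the COVID comment data set holds a record from the Study Drug Completion form, "then subject discontinued study drug due to COVID-19". If it holds one from the Study Completion form, "then subject discontinued study due to COVID-19". For discontinuations due to an adverse event, the programmer also checks whether that event is flagged as COVID-19. Section 4.1.2 puts the result in a separate listing of premature discontinuations.

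**The concern.** A keyword search attributes cause well only if the words are specific to that cause or the search is confined to the period when the cause was possible. Here some words are general and the period is open. The B/F/TAF group contributes data from its first randomized dose, so the comments searched include years in which COVID-19 could not have been the reason for a missed visit.

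Item 24 has the same weakness. It treats a mention as the cause. A comment that a subject moved away, and that the last call took place during lockdown, would be read as a COVID-19 discontinuation whatever reason the site recorded.

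What is at stake is modest. Section 4.4 is where the final report would show how far the pandemic disturbed attendance. Because its categories depend on the number of affected visits per subject, one false hit can move a subject from none to one, or from one to two.

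**Working it through.** The SAP states no COVID-19 count or percentage, so there is no figure to reproduce. The check has four steps.

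**1. Do the searched comments reach back before the pandemic?** Appendix 6 item 23 dates a creatinine calibration change to 1 July 2018 and says baseline samples were measured before it. SAP Section 3 bases all final tables on data collected on B/F/TAF, which for the B/F/TAF group start in the randomized phase. The documents give no pandemic start date; I assume none earlier than 1 January 2020.

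- From 1 July 2018 to 1 January 2020: 365 + 184 = 549 days; 549/7 = 78.4 weeks.
- Week 72 falls on day 504 and Week 84 on day 588 (SAP Table 3-1).
- So Weeks 4, 8, 12, 24, 36, 48, 60 and 72, at least eight scheduled visits for each B/F/TAF-group subject who stayed that long, were due before the assumed start.

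For subjects who switched from DTG + F/TAF, the tabulated data begin only with open-label dosing, so the exposure to this error is smaller.

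**2. What does Step 3 do with a hit?** With the COVID flag at 0, nothing is counted. With the flag at 1:

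| Virtual term found | Visit date missing | Result |
|---|---|---|
| no | no | not counted |
| no | yes | missed visit |
| yes | no | virtual visit |
| yes | yes | both rules met, no precedence stated |

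A keyword alone therefore never enters the count. But take a Week 36 visit, missed before the pandemic, with a comment about a family crisis. CRISIS is an exact match (distance zero), so the flag is 1; the visit date is missing, so the visit is classed as a COVID-19 missed visit. An early telephone contact whose comment contains both CRISIS and PHONE would be classed as virtual even with its date present. Nothing in Steps 1 to 3 rejects either case.

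**3. What does item 24 do with a hit?** Setting item 24 beside Section 4.1.2:

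- A subject who completed drug and whose comment mentions COVID-19 meets item 24 as written, but Section 4.1.2 confines the listing to premature discontinuations, so that subject should drop out.
- A subject who stopped early for another reason and whose comment mentions COVID-19 meets both, and is listed as a COVID-19 discontinuation.

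The adverse-event check does not remove the second case when the recorded reason is not an adverse event.

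**4. How much would it matter?** Take the planned 300 per arm (SAP Section 1.3). Let d be the share who left before the pandemic, assumed equal in both arms, with every remaining DTG subject switching. Then:

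- Section 4.4 denominator = 300 + 300(1 − d)
- still in the study = 600(1 − d)
- ratio = 2(1 − d)/(2 − d)

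| d (assumed) | Section 4.4 denominator | Still in study | Ratio | A 40% rate among those still in study is reported as |
|---|---|---|---|---|
| 5% | 585 | 570 | 0.974 | 39.0% |
| 10% | 570 | 540 | 0.947 | 37.9% |
| 20% | 540 | 480 | 0.889 | 35.6% |
| 30% | 510 | 420 | 0.824 | 32.9% |

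Over the same range, each subject wrongly moved from none to at least one adds between 100/585 = 0.17 and 100/510 = 0.20 percentage points. How many such subjects there are cannot be obtained from the documents.

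**The case against.** The best defence is that the rules are less loose than the word list suggests. A hit counts only with a missing visit date or a virtual term. Sites had standard wording for genuine cases. The list is given as examples and can be tuned, and the by-subject listing would expose an odd hit. The COVID comment data set is not specified in the documents, so it may already carry limits that cannot be seen.

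Much of this stands, but it does not close the gap. The missing-date condition does not protect a visit that really was missed, earlier and for another reason. Standard wording governs how genuine cases are recorded; it does not stop older comments being searched. Tuning words is no substitute for a date limit, and no review of hits is written. By contrast, the COVID-19 adverse event terms in Appendix 4 were reviewed by medical monitors.

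A reader might infer more, in three ways the documents do not support:

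- **That the COVID-19 counts and percentage are wrong.** No counts, false-hit rate or departure dates are given. False hits raise the percentage, while the whole-set denominator lowers it relative to subjects still in the study. The net direction is unknown.
- **That item 24 inflates a discontinuation count.** The SAP specifies only a listing, restricted to premature discontinuations.
- **That the denominator is an error.** It is stated openly and gives a correct percentage of all subjects in the set. It is not a rate among those at risk, and Section 4.4 does not call it one.

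**Conclusion.** The point holds as a risk of misclassification built into two stated rules. Under Appendix 5, a pre-pandemic missed visit whose comment contains a listed general word is counted as a COVID-19 missed visit. Under item 24, an early discontinuation for another reason can be listed as due to COVID-19. The Appendix 5 conclusion assumes only that the pandemic began after part of the follow-up, which the July 2018 date supports.

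The size cannot be computed. The 0.17 to 0.20 points per misclassified subject and the denominator ratios of 0.974 to 0.824 are illustrations from planned arm sizes and assumed departures.

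The consequence is confined to descriptive COVID-19 outputs. The missing-equals-excluded and missing-equals-failure analyses in Section 6.3.2.1 handle missing HIV-1 RNA without regard to cause, and no efficacy or inferential result uses these flags. This is a minor point, worth acting on because the repair is cheap.

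**What to change.** - **Appendix 5.** Count a missed or virtual visit as COVID-related only if its scheduled due date is on or after a fixed date: a stated pandemic start, or the issue date of the site COVID-19 supplement. The due date must be derived, because a missed visit has no visit date: from Study Day 1 for blinded-phase visits and from the End of Blinded Treatment Visit for open-label ones. State which label applies when both Step 3 rules are met, and review the hits that remain.
- **Appendix 6 item 24.** Require premature discontinuation on or after that date, and either agreement with the recorded reason or a review of the comment.
- **Section 4.4.** Keep the present denominator. Optionally, add a percentage among subjects still in the study on the fixed date.

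The cost is one derived due date per scheduled visit, a date filter, one or two added conditions and a short review of comments. No new data are needed. SAP Section 1 already provides for changes after finalization to be documented in the study report.
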